6.1 Participant Recruitment

Study participants will be recruited through the clinical practices of ULTRA investigators and among the general community of women seeking fibroid treatment. Advertisements for the study will be posted on the fibroid centers' and/or department website and in key clinical areas within our women's health clinics. We will also post advertisements in local newspapers and community boards. Study investigators will identify patients with symptomatic fibroids who meet the inclusion and exclusion criteria and invite them to participate in ULTRA. Study investigators will explain the Radiofrequency ablation procedure as well as the study protocol. Potential study participants will be offered alternatives to Radiofrequency ablation treatment as clinically indicated and available including medical management for heavy bleeding, myomectomy, hysterectomy, uterine artery embolization, and MR Guided Focused Ultrasound.

[figure not shown]
6.2 Informed Consent

The study aims and procedures will be explained initially by the study investigators during a fibroid consultation visit. A trained research coordinator will then confirm that the patient meets the inclusion and exclusion criteria and review in detail the study consent form and protocol with emphasis on the length of follow-up and required follow-up procedures. The study investigator will answer any additional questions about Radiofrequency ablation or study procedures. The study investigator will discuss with the participant the risk that the Radiofrequency ablation procedure cannot be performed at the time of surgery (e.g. due to dense pelvic adhesions) and inquire what alternative treatment options the participant would desire (e.g. an open abdominal myomectomy). The participant will then sign the study consent form. In addition, the participant will sign a standard surgical consent form unique to each study site that details the Radiofrequency ablation procedure, risks, benefits, and alternative therapies.

7.0 THE RADIOFREQUENCY ABLATION DEVICE

All study participants will undergo a standard Radiofrequency ablation procedure using the Halt System™. The Radiofrequency ablation Device is comprised of two primary components (Figure 1):

1. The Electrosurgical Radiofrequency Generator (Halt 2000): The generator is a nondisposable component that delivers radiofrequency energy through a Probe Extension Cable (TU1200) to a probe placed within the fibroid. The generator includes 3 accompanying components: 1) a pneumatic foot pedal to turn the generator on and off, 2) a medical grade power cord to

deliver AC power to the generator, and 3) a dispersive electrode pad set (TSP115) that provide the energy return path delivered through the probe.

2. The Electrosurgical Radiofrequency Probe (Tulip or TU1000): The probe is a hand piece with a trocar-pointed shaft. At the end of the shaft are 7 needle electrodes that are deployed within the fibroid. The probe connects to the Halt 2000 with the Radiofrequency Probe Extension Cable (TU1200).

The Halt 2000 can deliver up to 200W of power. An automated ablation algorithm sets the duration of ablation based on the volume of tissue to be treated calculated from the length of the deployed probes within the fibroid.

7.1 Preoperative Preparation

All study participants will undergo a preoperative complete blood count, type and screen, and pregnancy test (serum or urine HCG within 48 hours of surgery). In addition, all study participants will be evaluated preoperatively by a member of the anesthesia care team (MD or CNA) to determine individual risks of general anesthesia. Additional preoperative preparation will be left to the discretion of the treating gynecologist in accordance with the participants' medical history and the clinical practice and protocols of each study site.

7.2 The Radiofrequency ablation Procedure

The Radiofrequency ablation procedure will vary somewhat among study participants based on the size, number, and location of fibroids as well as the surgical protocols and practices at each study site. Gynecologists may select which laparoscopic port system is used and which laparoscopic entry procedure they prefer for the Radiofrequency ablation procedure. Any standard laparoscopic 10-12mm ultrasound probe may be used. However, all Radiofrequency ablation procedures will proceed with several uniform steps as follows:

1. Sequential compression devices are placed on the bilateral lower extremities.
2. Antibiotics are not given as surgical prophylaxis per ACOG guidelines for laparoscopy.
3. General anesthesia is induced.
4. A Foley catheter is placed in the bladder.
5. A pelvic exam is performed with note of the uterine size.
6. An IUD is removed if present.
7. A HUMI plastic uterine manipulator is placed in the uterus with the patient in dorsal lithotomy position (optional).
8. Grounding pads are placed on the bilateral thighs 1cm above the patella with good skin contact.
9. A 5mm umbilical port site is placed for a 5mm laparoscope.
10. A 10-12mm midline port site is placed for the ultrasound.
11. The ultrasound is used to locate and measure all uterine fibroids and fibroid measurements are recorded.
12. The Radiofrequency Probe is placed into the abdomen percutaneously under direct visualization.
13. The Radiofrequency Probe is used to perform the fibroid ablation following the Instructions for Use of the Radiofrequency ablation system. The ablation algorithm will guide the length of the ablation procedure. Care will be taken to avoid the pelvic sidewall, bladder, and bowel.

14. All fibroids visualized with intraoperative ultrasound are treated with the Radiofrequency Probe.
15. Submucosal fibroids are treated after removing the HUMI uterine manipulator. The HUMI uterine manipulator can be used to help position the Radiofrequency Probe in the fibroid, but then the manipulator is removed before heat is delivered to the fibroid.
16. The Radiofrequency Probe and laparoscopic ports are removed.
17. The 10-12 mm port site fascia may be closed at the discretion of the surgeon.
18. The skin is closed with surgical glue or sutures at the discretion of the surgeon.
19. The patient is discharged from the recovery room after meeting recovery room discharge criteria.
20. Discharge medications include nonsteroidal anti-inflammatories and narcotic analgesia at the discretion of the gynecologist.

7.3 Unanticipated Surgical Findings

At the time of surgery, unanticipated surgical findings may create an obstacle to performing the Radiofrequency ablation procedure (e.g. dense pelvic adhesions). In this case, the surgeon may elect to perform another fibroid treatment such as abdominal myomectomy or hysterectomy guided by the preoperative discussion with the participant regarding her desire under these circumstances. In addition, if an adnexal mass is visualized intraoperatively and the surgeon feels it should be removed, she/he may complete this surgery. Finally, if a subserosal or pedunculated fibroid is visualized that was felt to have a broad base but appears to have a narrow stalk, it may be removed via laparoscopic myomectomy.

7.4 Procedure Training and Support

Study investigators will be trained to perform the Radiofrequency ablation procedure during a one day in-service conducted by Halt Medical. The training includes didactic sessions and hands-on simulation of laparoscopic ultrasound and use of the Radiofrequency Probe. A trained Radiofrequency ablation physician employed by Halt Medical will be present in the operating room to provide technical support during the first 5 cases each investigator performs. This Radiofrequency ablation trainer can be present for additional cases at the request of the investigator as needed for additional support.

7.5 Use of Radiofrequency ablation Outside of The ULTRA Study

The procurement of Radiofrequency ablation to the UC Operating Rooms is through the UC policies and procedures for IRB approved clinical trials, not through the pathway for device use in general clinical practice. Therefore, there will be no use of Radiofrequency ablation at study sites outside of participants enrolled in ULTRA/ULTRA Registry. Study investigators will not use Radiofrequency ablation for patients undergoing procedures who are not enrolled in ULTRA/ULTRA Registry. Among study participants, investigators will only use Radiofrequency ablation according to the ULTRA protocol.

8.0 MEASURED VARIABLES

8.1. Outcome Variables

Outcomes will be measured at baseline prior to the Radiofrequency ablation procedure and at multiple time points for 3 years after the Radiofrequency ablation procedure. Questionnaires will be administered to evaluate patient-reported fibroid symptoms, operative outcomes, adverse events, the rate of re-intervention for fibroid symptoms, and surgeon self-assessment of skill and satisfaction. In the following section, outcome measurements are described in detail.

8.1.A Questionnaires to Assess Symptoms

These are validated questionnaires to assess the change in symptoms over time following the Radiofrequency ablation procedure.

1. **Uterine Fibroid Symptom-Quality of Life (UFS-QOL):** The UFS-QOL is a standardized questionnaire to evaluate fibroid-specific symptoms including heavy bleeding and urinary and bowel symptoms as well as the impact of fibroid symptoms on quality of life.^{4,5} The UFS-QOL has been used widely in studies of uterine preserving fibroid treatments including trials of Uterine Artery Embolization and MR Guided Focused Ultrasound.
2. **SF-36:** The SF-36 is a widely used, validated questionnaire to assess overall quality of health.⁶ There are 2 primary domains: Mental Health and Physical Health. The SF-36 has been used in multiple studies of women's health for a wide range of conditions including heavy uterine bleeding and symptomatic fibroids.
3. **Menstrual Impact Questionnaire (MIQ):** The MIQ is a validated questionnaire to evaluate the impact of heavy menstrual bleeding on quality-of-life.⁷ The MIQ has been used in trials of heavy bleeding that includes women with uterine fibroids.
4. **Overall Treatment Effect:** The Overall Treatment Effect used for this study is modified from a validated questionnaire to determine changes in symptoms following a medical intervention.⁸ The OTE consists of three questions that query women about whether symptoms have improved or not since treatment. These questionnaires have been compared with measures from the UFS-QOL among gynecologic patients.⁹ Three additional questions are generally linked to the OTE to assess overall patient satisfaction with treatment. This 6 question adapted OTE has been used in prior studies of women undergoing the Radiofrequency ablation procedure.
5. **Sexual Health Outcomes in Women Questionnaire (SHOW-Q):** This is a sexual functioning measure used to assess the impact of pelvic problems on various domains of sexual functioning for women's health studies.

8.1.B Perioperative Outcomes

Perioperative outcomes will be assessed during surgery, immediately after surgery in the recovery room, and postoperatively for 6 weeks. We will collect standard perioperative variables for a surgical procedure to evaluate safety and efficacy including the duration of surgery, recovery time, and adverse events. Table 1 outlines key perioperative outcomes. Adverse events are described in section 9.0.

Table 1. Perioperative Outcomes	
Intraoperative Outcomes	
 • Procedure time 
 *skin to skin time *total OR time • Fibroids detected by intraoperative ultrasound, not visualized on preoperative imaging 
 *Total number *Location of each fibroid *3 dimensions in cm of each fibroid • Estimated blood loss • Unanticipated operative findings • Adverse events • Mechanical malfunction with equipment
Immediate Postoperative Outcomes (Recovery Room)	
 • Unplanned/unanticipated intraoperative procedures • Time in recovery room • Hospital admission • Gynecologist rating of procedure difficulty • Participant rating of pain on Visual Analogue Scale • Adverse events
Delayed Postoperative Outcomes (Within 6 weeks of Radiofrequency ablation)	
 • Days to return to normal activities • Days to return to work if applicable • Clinic or hospital visits related to surgery of fibroid symptoms • Adverse events • Pregnancies and pregnancy outcomes

8.1.C Long Term Operative Outcomes

Long term outcomes related to surgery will include measures related to treatment failure, long-term morbidity, and pregnancy as follows:

1. Treatment Failure: We will ask participants to report any additional fibroid treatment including medical management for fibroid-related symptoms, myomectomy, hysterectomy, uterine artery embolization, MR Guided Focused Ultrasound, endometrial ablation, dilation and curettage, or any new and emerging fibroid treatments.
2. Adverse Events
3. Pregnancy and pregnancy outcomes: Participants will report all known pregnancies following Radiofrequency ablation. For each pregnancy, we will query participants about whether the pregnancy resulted in a miscarriage, abortion, or continued pregnancy. For continued pregnancies, we will ask participants to report obstetric outcomes including gestational age at birth, mode of delivery (vaginal or cesarean), and complications (e.g. placenta previa, placental abruption, preeclampsia).

8.1.D Schedule of Outcome Assessment

Outcomes will be assessed at varying timepoints from before the Radiofrequency ablation procedure to 3 years following the procedure (Table 2). In-person study visits will occur prior to surgery at the Screening Visit (SV), on the day of surgery called the Baseline Visit (BV), and 6

weeks following surgery. All other follow-up data will be collected through mailed or on-line questionnaires, or phone interviews.

Table 2. Schedule of Outcome Assessment and Participant Renumeration													
	SV	BV	2 day	1 wk	3 wk	6 wk	3 mo	6 mo	12 mo	18 mo	24 mo	30 mo	36 mo
In person visit	X	X				X							
Questionnaires to Assess Symptoms	X			X		X	X	X	X	X	X	X	X
Perioperative Outcomes		X	X	X	X	X							
Long Term Operative Outcomes							X	X	X	X	X	X	X

8.2 ADDITIONAL MEASUREMENTS

We will collect additional subjective and objective measurements that will be used to:

1) describe the study population and 2) serve as confounding factors in multivariable analysis of the change in fibroid-related symptoms over time.

8.2.A Preoperative Assessment, Study Participants

At baseline, we will query women about their general and reproductive health and obtain baseline data on fibroid size, number, and location as outlined in Table 3.

Table 3. Preoperative Assessment, Study Participants	
Participant-Reported Baseline Measures	
 Demographic characteristics (age, race/ethnicity, education) Medical and surgical history Reproductive history (including pregnancy and pregnancy outcomes) Medication use Complementary and alternative therapy use Desire for future fertility
Objective Baseline Measures	
 Weight Height Uterine size by bimanual exam Vital signs Fibroid characteristics on ultrasound or MRI 
 *Total number *Location of each fibroid *3 dimensions in cm of each fibroid Hematocrit/Hemoglobin (if available)

8.2.B Preoperative Assessment, Study Gynecologists

At baseline, participating gynecologists will be queried regarding their practice setting, training, and laparoscopic skill and experience as outlined in Table 4.

Table 4. Preoperative Assessment, Study Gynecologists	
General Characteristics and Training	
 • Demographic characteristics (age, race/ethnicity, gender) • Work history • Year completed residency • Fellowship/Advanced Training in Laparoscopy • Surgical volume • Practice setting (e.g. fibroid specialty clinic)
Surgical Skill and Competence	
 • Self-rated comfort level with various laparoscopic procedures • Prior use of intra-operative ultrasound and/or radiofrequency ablation

9.0 ADVERSE EVENTS

We will assess adverse outcomes in the perioperative period (the day of surgery until 6 weeks following surgery) as well as each study visit for 3 years after the procedure. We will ask the treating gynecologist about adverse events within 6 weeks of surgery. After 6 weeks when the participants may not have regular contact with the gynecologist, we will query study participants directly about adverse events.

We will list the known potential adverse events following Radiofrequency ablation treatment and ask for a yes/no response to determine whether it occurred. In addition, we will evaluate potential unknown adverse events by ask the treating gynecologists the following question "Have there been any adverse outcomes associated with the Radiofrequency ablation treatment that are not listed in this form?" Study participants will be asked "Have there been any negative changes in your health since your last study visit?"

Each reported adverse event will have a case report form that documents further details related to the adverse event including when it occurred, how it was diagnosed and treated, and the final clinical outcome.

Potential adverse events related to undergoing Radiofrequency ablation to be reported by the treating gynecologist within 6 weeks of surgery are:

1. Intraoperative injury to genitourinary or gastrointestinal tract, or other abdominal or pelvic organs
2. Blood transfusion
3. Unplanned visit to the Emergency Room or admission to the hospital
4. Pulmonary embolus or deep vein thrombosis
5. Major nerve injury with sensory or motor deficits
6. Infection at the site of the skin incision
7. Infection of the uterus or fibroid
8. Urinary tract infection
9. Hematoma at the site of trochar placement
10. Hernia at the site of trochar placement

11. Skin burn at the site of dispersive pad on bilateral thighs
12. New onset pelvic pain that persists >6 weeks after Radiofrequency ablation procedure

Potential adverse events related to undergoing Radiofrequency ablation to be reported by study participants from 6 weeks to 3 months after surgery are:

1. Hernia at the site of trochar placement
2. New onset pelvic pain

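### Section 9.0 names only the treating gynecologist as adverse-event respondent for the first 6 weeks, so complications unknown to the surgeon may be under-counted

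*Combined protocol and SAP*

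**What the plan says.** Section 9.0 divides adverse-event reporting by time and respondent.

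- **Up to 6 weeks.** "We will ask the treating gynecologist about adverse events within 6 weeks of surgery". The 12-item yes/no list is headed as events "to be reported by the treating gynecologist within 6 weeks of surgery are". The gynecologist also gets an open question: "Have there been any adverse outcomes associated with the Radiofrequency ablation treatment that are not listed in this form".
- **After 6 weeks.** "After 6 weeks when the participants may not have regular contact with the gynecologist, we will query study participants directly about adverse events". The participant list has two items, trocar-site hernia and new pelvic pain, and is headed "to be reported by study participants from 6 weeks to 3 months after surgery are". The open participant question is "Have there been any negative changes in your health since your last study visit".

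Other sections bear on the same period. Section 8.1 says in general terms that questionnaires cover adverse events, without naming who answers or when. Table 1 (Section 8.1.B) lists adverse events among the outcomes within 6 weeks, together with "Clinic or hospital visits related to surgery of fibroid symptoms", and the section refers to Section 9.0 for adverse events. Table 2 (Section 8.1.D) marks perioperative outcomes on the day of surgery, at 2 days, and at 1, 3 and 6 weeks. Of these, only the day of surgery and week 6 are in-person visits. For the rest, "All other follow-up data will be collected through mailed or on-line questionnaires, or phone interviews".

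**The concern.** Section 7.2 has the patient discharged from the recovery room, and Table 2 has no further in-person study visit until week 6. Several of the 12 items can be treated elsewhere or noticed only by the woman: an emergency visit, a urinary or wound infection, a port-site hematoma, a skin burn under a dispersive pad. Item 12, pelvic pain lasting beyond 6 weeks, depends on what she reports. If she is not asked, such an event enters the record only if the surgeon happens to learn of it.

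The two open questions also differ in scope. The gynecologist's is limited to outcomes linked to the ablation, so the respondent makes an attribution judgement first. The participant's has no such limit. The respondent in the early period will usually be the operator, since Section 12.0 has each investigator performing 10 procedures, and secondary objective 3 assesses gynecologists' performance during the learning curve.

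At stake are the complication component of secondary objective 2 and the adverse-event item of DSMB review (Section 10.0). Section 4.0 also intends the pilot's procedures as a template for later comparative trials, so a gap here could be carried forward.

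**Working it through.** The plan gives no figure for adverse-event ascertainment, so there is none to reproduce. The check compares the text and then gives an illustration on assumed values.

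**Who is asked, and over what period**

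1. *Day 0 to week 6, Section 9.0.* The named respondent for both the list and the question on unlisted events is the treating gynecologist. No participant question is stated for this period.
2. *Day 0 to week 6, Tables 1 and 2.* Adverse events and surgery-related visits are among the outcomes, and contacts are scheduled at 2 days and at 1, 3 and 6 weeks. No adverse-event respondent is named. Because Section 8.1.B refers to Section 9.0, following the cross-reference leads back to the gynecologist.
3. *First scheduled contact after week 6.* Table 2 puts this at 3 months. The last study visit before it is week 6, so the open question then covers week 6 to month 3. The two-item list covers the same interval. Neither recovers an event from the first 6 weeks.
4. *From visit to adverse event.* Item 3 of the gynecologist's list covers unplanned emergency visits and hospital admissions, and Table 1 separately collects surgery-related clinic or hospital visits. Section 9.0 requires a case report form for each reported adverse event, but nothing says that a visit reported under Table 1 counts as one. An event that leads to no visit does not use this route at all.

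A site working from Section 9.0 would not ask the woman before week 6. A site working from Tables 1 and 2 might. With five sites, ascertainment could differ for that reason alone.

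**Illustration**

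Inputs: N = 100 (Section 3.0); p = share of women with a listed event by week 6; s = share of those events known to the surgeon. The documents give neither p nor s, so both are assumptions, and the calculation applies only if participants are not asked.

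Expected missed events = N × p × (1 − s). Chance of at least one = 1 − [1 − p(1 − s)]^N.

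- p = 5%, s = 95%: 100 × 0.05 × 0.05 = 0.25 missed; 1 − 0.9975^100 = 22%.
- p = 10%, s = 80%: 100 × 0.10 × 0.20 = 2.0 missed; 1 − 0.98^100 = 87%.
- p = 20%, s = 60%: 100 × 0.20 × 0.40 = 8.0 missed; 1 − 0.92^100 is nearly 100%.

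In the middle case the recorded count is 8 instead of 10 per 100. The exact (Clopper-Pearson) 95% intervals are 3.5–15.2% for 8/100 and 4.9–17.6% for 10/100.

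**The case against.** A reader might infer that complications unknown to the surgeon are never elicited, and that no adverse-event question put to the woman covers day 0 to week 6. The documents do not support that. Section 8.1 says questionnaires evaluate adverse events, Table 1 includes them within 6 weeks, and Table 2 schedules contacts in that period, partly by questionnaire or phone. The sentence introducing the open participant question gives no start date. If it were asked at the in-person week-6 visit, the previous in-person visit would be the day of surgery and the look-back would cover the whole period. Care received elsewhere also has routes into the data, through item 3 of the gynecologist's list, the Table 1 visits and the resource-utilization analysis in Section 12.0. This part of the objection stands: the plan leaves early participant questioning unstated and does not rule it out.

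The plan also gives a reason for its split. It changes respondent when regular contact with the gynecologist may end, which presumes such contact before then, and some items, such as intraoperative injury, are best known to the clinician. That justifies asking the gynecologist. It does not justify leaving the woman out, given that Table 2 has no in-person visit between the day of surgery and week 6.

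The consequences should not be stretched. Adverse events are one of four DSMB review items, although the intraoperative and immediate postoperative outcomes, a second item, also include them. Secondary objective 2 covers duration, blood loss, pain and recovery as well as complications. Nothing in the documents shows that under-reporting would differ between surgeons. The future trial is planned as randomized, with ULTRA supplying effect sizes and standard deviations for its sample size, so it would not rest on this event count.

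**Conclusion.** The point holds as a risk of under-ascertainment. Section 9.0 states a rule for the first 6 weeks that names the gynecologist alone, the cross-reference in Section 8.1.B points to that rule, and the first participant questioning it clearly provides for, at 3 months, starts its look-back at week 6. The conclusion depends on Section 9.0 being applied as written, and the documents do not establish that participants go unasked.

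The size is unknown. The assumed cases run from 0.25 to 8 missed events per 100 women, with about 2 in the middle case. A shortfall of 2 in 10 is small against the sampling error of a 100-woman study, but it acts in one direction and enrolling more women would not remove it. The change is worth making because it is cheap and concerns a safety outcome. No result of the trial is shown to be invalid.

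**What to change.** In Section 9.0, keep the gynecologist form and add participant questioning at the existing 2-day, 1-week, 3-week and 6-week contacts:

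- Ask the yes/no items that a participant can answer, together with the open question. Items such as intraoperative injury can stay with the gynecologist alone.
- At week 6, word the look-back as running from the day of surgery.
- Count an event if either source reports it, complete the Adverse Event Case Report Form for it, and record the source so that the DSMB report can show it.
- State when a clinic or hospital visit reported under Table 1 is to be assessed as a possible adverse event.
- Align Sections 8.1.B and 8.1.D by naming the respondent at each contact.

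The cost is a few extra questions at contacts already scheduled, some follow-up of minor events, and possibly a less favourable reported complication rate.

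### The only open question for unknown harms in the first 6 weeks is limited to outcomes the gynecologist associates with the ablation, so a narrow class of unlisted events has no clear route to being recorded

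*Combined protocol and SAP*

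**What the plan says.** Section 9.0 (Adverse Events) splits ascertainment at 6 weeks. For the first window: "We will ask the treating gynecologist about adverse events within 6 weeks of surgery". For the second: "After 6 weeks when the participants may not have regular contact with the gynecologist, we will query study participants directly about adverse events".

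In the first window the gynecologist has two instruments. One is a 12-item checklist: "We will list the known potential adverse events following Radiofrequency ablation treatment and ask for a yes/no response to determine whether it occurred". Item 3 is "Unplanned visit to the Emergency Room or admission to the hospital". The other is an open question whose purpose is stated: "we will evaluate potential unknown adverse events by ask the treating gynecologists the following question". The question is "Have there been any adverse outcomes associated with the Radiofrequency ablation treatment that are not listed in this form".

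The participants' open question is "Have there been any negative changes in your health since your last study visit".

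On documentation, the section says: "Each reported adverse event will have a case report form that documents further details related to the adverse event including when it occurred". It then names diagnosis, treatment and final outcome. Section 9.1 grades severity. Neither section mentions an assessment of relatedness.

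**The concern.** An unknown harm is, almost by definition, one that the clinician does not yet connect with the device. A question that admits only outcomes *associated with* the ablation asks for that connection before anything is written down. The usual order is to record the event first and judge its cause afterwards, because an event left out at the first step cannot be recovered at the second.

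This trial has reasons to care. It is single-arm (section 3.0), so no control group can reveal an excess. Section 1.0 describes outcome data on the procedure as limited. Each investigator's 10 cases are a learning period (section 12.0, Sample Size Calculation). Section 4.0 also makes the procedures and measurements a template for later comparative trials, and a question tied to the ablation could not be put unchanged to a myomectomy arm.

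**Working it through.** The documents give no figure for adverse-event detection, so there is nothing to reproduce. The check is first of the text, then of scale under stated assumptions.

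**Step 1. Routes by which an unlisted event in the first 6 weeks could be recorded.**

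- *Checklist, section 9.0.* Each item is asked as occurred or not, with no attribution condition. An unexpected event that leads to an unplanned emergency visit or an admission is flagged by item 3, whatever its cause.
- *Table 1, section 8.1.B.* Unanticipated operative findings, unplanned intraoperative procedures, equipment malfunction and hospital admission are collected without an attribution condition. The general adverse-event entry has no question of its own, because the section refers back to 9.0. The entry for later clinic or hospital visits is tied to surgery or fibroid symptoms, so it carries a condition too.
- *Open question to the gynecologist.* It is limited to outcomes associated with the ablation.
- *Open question to the participant.* It has no condition, but section 9.0 assigns direct participant querying to the time after 6 weeks, and the question looks back only to the last study visit. At 3 months, the next contact in Table 2, that naturally means the 6-week visit and not the operation.
- *Contacts at 2 days, 1 week and 3 weeks (Table 2).* Perioperative outcomes are due at these times, but the documents give no unconditional open question for them.

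**Step 2. What is left over.** An event falls through if it is not on the checklist, leads to no emergency visit or admission, fits no Table 1 item, and is not linked to the ablation by the gynecologist. Events managed in clinic or by telephone are the natural examples.

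**Step 3. Scale, for events in that gap only.** Inputs:

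- n = 100 women (section 3.0).
- p = true proportion of women with the event. Assumed; not in the documents.
- a = share of cases the gynecologist attributes to the ablation. Assumed; not in the documents.

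With women independent and no other route of capture, the chance that at least one case is recorded is 1 − (1 − p × a)^100.

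For p = 0.03:

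- a = 1: 1 − 0.97^100 = 0.952
- a = 0.5: 1 − 0.985^100 = 0.779
- a = 0.25: 1 − 0.9925^100 = 0.529

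Across a range of p:

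| Assumed p | a = 1 | a = 0.5 | a = 0.25 |
|---|---|---|---|
| 1% | 63.4% | 39.4% | 22.1% |
| 2% | 86.7% | 63.4% | 39.4% |
| 3% | 95.2% | 77.9% | 52.9% |

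The a = 1 column is what an unconditional question would achieve if every case were reported.

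**The case against.** The strongest reply is that the gap is small and depends on a strict reading.

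- *Associated with* need not mean caused by; it can mean occurring with or after treatment. Section 9.0 itself uses such terms loosely: it heads the checklist as events related to undergoing the ablation, then includes any unplanned emergency visit or admission. This stands as a possible reading. It does not dispose of the point, because with 10 investigators (section 12.0) an ambiguous condition can be applied in different ways.
- A reader might infer that any event not attributed to the ablation goes unrecorded. The documents do not support that. The checklist and several Table 1 items have no attribution condition, and section 9.2 requires rapid reporting of Grade 4 or 5 adverse events without one. What remains is likely to be mostly lower-severity events.
- A reader might infer that the adverse event form has no relatedness field. The content in section 9.0 is introduced by *including*, so the list is open, and the form itself is not among the documents. One can say only that the protocol does not mention relatedness.
- A reader might infer that later events will be over-counted, or that early and late rates will be wrongly pooled. Recording every negative change in health is broad capture, not over-counting. No section plans to pool or compare the two windows: section 12.0 plans descriptive reporting, and sections 8.1.B and 8.1.C keep perioperative and long-term outcomes apart.
- A reader might infer that the monitoring board sees only filtered data while operations are under way. Under section 9.2 its reports cover all adverse events, which include the checklist events, and under section 10.0 it also reviews the intraoperative and immediate postoperative outcomes. Only the residual class in Step 2 could be missing.

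The objection therefore narrows the concern considerably. It does not show an unconditional open question for the first 6 weeks.

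**Conclusion.** The concern holds in a limited form. The plan's one open instrument for unknown harms in the first 6 weeks carries a condition at odds with its stated purpose, and the participant question used later does not. The two windows therefore differ in scope as well as in who reports, and anyone who sets early and late unlisted events side by side should know that.

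The size cannot be derived from the documents. Under the assumed values above, for events in the gap, the chance of seeing at least one case of a 3% event falls from 95% to 78% or 53%, and of a 2% event from 87% to 63% or 39%. Both the rates and the attribution shares are assumptions, so the figures show how sensitive detection is to the condition and do not estimate what will be lost.

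This is a cheap improvement to safety ascertainment, not a flaw that undermines the trial's safety data as a whole.

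**What to change.** 1. Reword the gynecologist's open question along these lines: *Has the participant had any adverse health event since surgery that is not listed on this form, whether or not you think it is related to the procedure?* This gives the first window the same unconditional scope as the participant question already has.
2. State in section 9.0 that relatedness is recorded as a separate item on the adverse event form (for example device, procedure, fibroid disease, unrelated). If the form already has such an item, a sentence in the protocol is enough.
3. State in section 12.0 that all events, and separately those judged related, will be reported for each window.

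The cost is one reworded question, at most one added form item, and some additional unrelated events to document.
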